### **9.3.2 Exclusion Criteria**

1. Subjects will be ineligible if, in the opinion of the Investigator, they are unlikely to comply with the study protocol or have a concomitant disease or condition that could interfere with the conduct of the study or potentially put the subject at unacceptable risk.

The exclusion criteria (except those related to screening) of protocol HZNP-TEP-301 also apply to this open-label extension study.

### **9.3.3 Removal of Subjects from Therapy or Assessment**

All subjects are free to withdraw from study participation at any time, for any reason, and without prejudice to their further medical care. In addition, the Investigator may terminate a subject from the study at any time. The primary reason for discontinuation from the study and/or study drug should be recorded on the eCRF using one of the following categories:

- Adverse Event. The subject experiences an AE that imposes an unacceptable risk to the subject's health, or the subject is unwilling to continue because of an AE. AEs requiring permanent study drug discontinuation per the protocol include:
  - A drug-related anaphylactic reaction.
  - A persistently severe drug-related AE that does not abate to mild or moderate intensity at least 2 weeks prior to the next scheduled dose.
  - Severe drug-related hyperglycemia (e.g., blood glucose > 250 mg/dL) that does not abate to mild or moderate intensity with anti-diabetic treatment (dose may be skipped up to 2 times prior to permanently discontinuing study drug; see [Section 9.4.6.3.2](#) for details).
  - Diagnosed or suspected IBD (e.g., diarrhea with or without blood or rectal bleeding associated with abdominal pain or cramping/colic, urgency, tenesmus, or incontinence for more than 4 weeks without a confirmed alternative diagnosis OR

endoscopic or radiologic evidence of enteritis/colitis without a confirmed alternative diagnosis).

- Lack of Efficacy. Removal of a subject from the study is at the discretion of the Investigator and may occur if the Investigator determines that study drug administration is not benefitting the subject and eye symptoms linked to progressing disease worsen posing an unacceptable risk to the subject. The specific care of the subject is best determined by the Investigator and managing physician(s) involved in the subject's care and may require removal from the study. All subjects are free to withdraw from study participation at any time, for any reason, allowing them to receive any specific treatment for TED that is considered necessary per their treating physician and local standard of care.
- Non-Compliance with Study Drug/Other/Protocol Deviations. The subject has a significant protocol deviation, does not comply with study drug administration schedule, or fails to adhere to other study requirements as stated in the protocol.
- Lost to Follow-Up. The subject does not return to the clinic for scheduled assessments, and does not respond to the site's attempts to contact the subject.
- Voluntary Withdrawal. The subject wishes to withdraw from the study. The clinical site should attempt to determine the underlying reason for the voluntary withdrawal and document it on the eCRF; if the underlying reason is documented as an AE or lack of efficacy, the category of withdrawal should be marked in the corresponding category and not as voluntary withdrawal.
- Study Terminated by Sponsor. The Sponsor, IRB/IEC, or regulatory agency terminates the study.
- Pregnancy.

When treatment is complete, subjects will undergo the scheduled Week 24 assessments.

Subjects who were proptosis non-responders in HZNP-TEP-301 will participate in the Follow-Up Period. Subjects who enter the Follow-Up Period but prematurely discontinue study participation prior to Month 12 will return for a final visit and undergo the scheduled Month 12 assessments prior to study discharge. Subjects who discontinue due to an AE should be followed until resolution or stabilization of the AE, or an adequate explanation for the event is obtained.

Subjects who relapsed during the HZNP-TEP-301 study will not participate in the Follow-up Period.

Subjects who complete the study (Month 12 Visit for proptosis non-responders in Study HZNP-TEP-301 and Week 24 Visit for subjects who relapsed during the Follow-up Period in Study HZNP-TEP-301) will be contacted 6 and 12 months after the last visit via phone or email by research staff to enquire if any treatment for TED has been received since last study contact.

### 9.3.4 Criteria for Responders Who Relapse

If subjects met the response criteria at Week 24 of HZNP-TEP-301 but subsequently experience a disease relapse during the 48-week Follow-Up Period of the lead-in study, they will have the option to enter this open-label extension study (HZNP-TEP-302) and receive 8 infusions of teprotumumab. The criteria to determine relapse is the following:

- Increase in proptosis of  $\geq 2$  mm in the study eye since Week 24 of HZNP-TEP-301, or
- An increase in CAS of  $\geq 2$  points since Week 24 with an absolute CAS of  $\geq 4$  in the study eye following Week 24 of HZNP-TEP-301.
- In addition to one of the bullet points above, the Investigator should also consider the subject's symptomology to ensure a relapse has occurred (e.g., new onset of double vision).

### 9.3.5 Replacement Policy

#### 9.3.5.1 Subjects

No subject prematurely discontinued from the study for any reason will be replaced.

#### 9.3.5.2 Centers

A center may be closed and/or replaced for the following administrative reasons:

- Poor protocol adherence.

## 9.4 Treatments

### 9.4.1 Treatments Administered

All study drug dosing will be performed at the clinic under the supervision of clinic staff. Subjects will receive 8 infusions of teprotumumab (10 mg/kg on Day 1 followed by 20 mg/kg q3W for the remaining infusions) in an open-label fashion.

The infusion rate may be reduced and the dose may be interrupted or held based on tolerability (see [Section 9.4.6.3.2](#) for details). The first and second infusions will be administered over approximately 90 minutes (but not less than 80 minutes). Subsequent infusions will be administered over approximately 60 minutes (but not less than 50 minutes), providing there are no significant infusion-associated events.

### 9.4.2 Identity of Investigational Product

Teprotumumab (HZN-001) is a fully human anti-IGF-1R mAb. The physiochemical properties were previously presented in [Section 7.1.3.1](#). Teprotumumab will be provided in single-dose 20 mL glass vials as a freeze-dried powder containing, in addition to the drug substance, 20 mmol/L histidine-histidine chloride, 250 mmol/L trehalose, and 0.01% polysorbate 20 (w/w).

Prior to administration, each vial containing 500 mg teprotumumab freeze-dried powder will be reconstituted with 10 mL of water for injection. The resulting solution has an approximate concentration of 50 mg/mL teprotumumab. The reconstituted teprotumumab solution must be further diluted in 0.9% (w/v) sodium chloride (NaCl) solution prior to administration (see [Section 9.4.6.3](#) for details).

#### **9.4.3 Labeling**

Study drug packaging will be in compliance with Sponsor/CRO standard procedures and will meet all local requirements.

Upon arrival of investigational products at the site, the investigational pharmacist or site personnel not assigned to the study should check them for damage and verify proper identity, quantity, integrity of seals, and temperature conditions, and report any deviations or product complaints to the monitor/Sponsor upon discovery.

#### **9.4.4 Storage**

Recommended storage conditions for the freeze-dried teprotumumab drug product are between 2°C to 8°C (36°F to 46°F), protected from light. Storage at ambient temperature of the reconstituted teprotumumab solution should be limited to 4 hours. For batch-specific information on shelf-life, see the packaging.

The IV infusion should be administered at room temperature (20°C to 24°C [68°F to 75°F]). The diluted product should be used within 4 hours of preparation. However, if not used within 4 hours, and if dilution has taken place under controlled and validated aseptic conditions, the infusion solution can be stored for up to 24 hours at 2°C to 8°C (36°F to 46°F). An Investigational Pharmacy Manual will be provided to all sites and further describe these processes in detail.

At the clinic, all study medications must be stored in a secure area with limited access, and a daily temperature log of the drug storage area will be maintained every working day; deviations from the specified temperature range will be reported as protocol deviations.

#### **9.4.5 Drug Accountability**

The Principal Investigator at each site is responsible for the control of all study medication and delegating infusion bag preparation and drug accountability responsibilities to a pharmacist (or designee in accordance with institutional policies and local regulations), who must maintain adequate records of the receipt and disposition of all study medication shipped to the study center. Records will include receipt dates, condition at time of receipt, quantities received, quantities dispensed, quantities returned or destroyed, and the identification numbers of the subjects who received study medication.

As permitted by site policy, all empty, partially empty, and full vials of study drug must be retained by the study center under locked storage until drug accountability has been completed. Periodically throughout the study and at the conclusion of the study, inventory checks and

accountability of study materials will be conducted by a representative of the Sponsor. Once accountability is completed, the Sponsor's representative will authorize the return of study medication (all used, partially used, and unused vials) to [REDACTED]. The completed Drug Accountability and Drug Return/Destruction Record(s) will be returned to the CRO manager. The Investigator's copy of the Drug Accountability and Drug Return/Destruction Record(s) must document accurately the return of all study drug supplies and be maintained by the pharmacist or designee until the study is complete and the database is locked. Records will also include disposition dates and quantities returned to the designated facility.

#### **9.4.6 Study Drug Administration and Timing of Dose for each Subject**

##### **9.4.6.1 Description of Clinical Supplies**

[REDACTED] will supply study drug to clinical sites. Ancillary supplies for dosing will be provided by the study site (i.e., infusion bags containing normal saline, infusion administration sets, syringes, needles, alcohol swabs, gauze pads, bandages, and biohazard containers for safe storage of used needles and syringes).

##### **9.4.6.2 Determination of Dose Volume**

The volume of study drug to be administered will be determined by the electronic data capture (EDC) system and will be based on the subject's weight. The first dose will be 10 mg/kg, and subsequent doses will be 20 mg/kg. Weight will be measured on Day 1 and Weeks 12 and 24 during the Treatment Period. The dose on Day 1 may be based on the weight determined at the most recent clinic visit, provided the most recent visit was within the prior 3 weeks. The doses on Week 3 through Week 9 will be based on the weight determined on Day 1. The weight used in the Week 12 dose calculation can be the weight determined on Day 1 or the weight obtained at Week 12. The weight obtained at Week 12 can be used to adjust the dose beginning at Week 12 or Week 15 through Week 21, as appropriate.

##### **9.4.6.3 Details Concerning Timing and Dose Administration**

###### **9.4.6.3.1 Preparation and Administration of Teprotumumab**

Teprotumumab will be prepared by the site pharmacist or designee in accordance with institutional policy and local regulations. Each vial of teprotumumab will be reconstituted with 10 mL of water for injection. The resulting solution will have an approximate concentration of 50 mg/mL teprotumumab antibody. Reconstituted teprotumumab solution will be further diluted in 0.9% (w/v) sodium chloride (NaCl) solution prior to administration by the site pharmacist or designee.

Doses up to 1800 mg will be administered in a total infusion volume of 100 mL, and those above 1800 mg will be administered in a total infusion volume of 250 mL. To maintain a constant volume in the infusion bags, a volume equal to the volume of teprotumumab to be placed into the infusion bag will be first removed from the infusion bag using a sterile syringe and needle. The appropriate volume of reconstituted drug product solution based on the subject's dose and body weight will be withdrawn and the teprotumumab drug product solution will be diluted with normal saline (0.9% NaCl) in the infusion bag.

The IV infusion is to be administered at room temperature (20°C to 24°C [68°F to 75°F]). The diluted product should be used within 4 hours of preparation. However, if not used within 4 hours, and if dilution has taken place under controlled and aseptic conditions, the infusion solution can be stored for up to 24 hours at 2°C to 8°C (36°F to 46°F).

No incompatibilities have been observed with:

- administration sets with product contact surface of polyethylene, polyvinyl chloride (PVC), or polyurethane
- inline filters with product contact surface of polyether sulphone
- IV bags (0.9% sodium chloride) with product contact surface of polyolefin or PVC.

In-line filters are not required, but if a hospital is routinely using them, in-line filters with a 0.2 µm pore size should be utilized.

Exposure of the solution to direct sunlight should be avoided.

All parenteral products should be visually inspected for particulates before administration.

Partially used vials should not be re-used.

The first and second IV infusions on Day 1 and Week 3 will be administered over approximately 90 minutes (but not less than 80 minutes) for all subjects; subsequent infusions may be administered over a shorter time period (approximately 60 minutes, but not less than 50 minutes) in the absence of any infusion-associated events. All subjects will be monitored for AEs from the start of infusion through 60 minutes after infusion completion for the first 3 doses; the monitoring period for subsequent doses may be reduced to 30 minutes after infusion completion for subjects who do not experience infusion-associated events.

#### **9.4.6.3.2 Dose Modifications, Interruptions, and Delays**

Subjects will be monitored for immediate infusion-associated events (e.g., nausea, vomiting, facial flushing, warmth, dyspnea, dizziness, hypertension, hypotension, pruritus) and delayed infusion-associated events (e.g., rash). If immediate infusion-associated events are noted, the infusion rate will be slowed or interrupted, symptomatic treatment (e.g., antipyretics, antihistamines, beta-agonists, oxygen, IV fluid) will be administered, and vital signs (temperature, blood pressure, pulse, and respiratory rate) will be monitored every 5 minutes until stable and then every 15 minutes for 2 additional determinations. The infusion may be restarted upon complete resolution of symptoms; however, study drug dosing will be permanently discontinued if the event is an anaphylactic reaction.

If delayed infusion-associated events are noted, subjects may continue dosing at the Investigator's discretion; however, if a rash worsens following repeated dosing or other signs of serum sickness (e.g., delayed fever, myalgias, arthralgias) are present, study drug dosing will be permanently discontinued.

Following the appearance of either immediate or delayed infusion-associated events, subsequent doses may be pre-treated with diphenhydramine (1 to 1.25 mg/kg IV; maximum of 50 mg), ranitidine (50 mg IV), famotidine (0.5 mg/kg IV), dexamethasone (0.4 mg/kg IV; maximum of 20 mg), and/or acetaminophen (500 mg). All subsequent infusions will be administered over approximately 90 minutes (but not less than 80 minutes) with vital signs monitored every 15 minutes from the start of the infusion through 60 minutes after infusion completion.

In general, the decision to continue dosing should take into consideration the potential benefit and risk to a subject.

Any severe drug-related AE must revert to mild or moderate in intensity at least 2 weeks prior to the next scheduled dose in order for the dose to be administered; if the AE remains severe in intensity within 2 weeks of the next scheduled dose, the subject will be withdrawn from treatment.

Increase in blood glucose is a known AE observed in previous clinical trials with teprotumumab and other IGF-1R antagonists and is known to respond to treatment. Since a referral for treatment of hyperglycemia may take some time, if the Investigator considers it appropriate to continue the subject in the study, the next scheduled infusion visit may be skipped to allow modified anti-diabetic treatment to show its activity and hyperglycemia to return to mild/moderate level before dosing. The subject would then be dosed at the next scheduled visit (i.e., 6 weeks after the previous infusion). Fasting blood glucose levels must return to mild/moderate severity before the next scheduled infusion. The above process of withholding a scheduled infusion will be permitted only twice during the study.

Any changes to the scheduled dosing interval (q3W) or adjustments in the infusion rate should be reported to the Sponsor/CRO.

#### **9.4.7 Method of Assigning Subjects to Treatment Groups**

All subjects will receive teprotumumab in this open-label extension study.

#### **9.4.8 Masking and Unmasking**

This is an open-label extension study.

In order to maintain the study mask in HZNP-TEP-301, all subjects in this open-label extension study will undergo the same dosing regimen of teprotumumab (10 mg/kg on Day 1 followed by 20 mg/kg q3W for the remaining 7 infusions), regardless if they received teprotumumab or placebo in HZNP-TEP-301.

#### **9.4.9 Concomitant Therapy and Restricted Medications**

Local supportive measures for TED, simple analgesics (e.g., acetaminophen, non-steroidal anti-inflammatory therapies), and medications/supplements for conditions other than TED are permitted during the study. Topical corticosteroids for conditions other than TED are allowed;

however, oral corticosteroid use during the study is restricted to subjects who experience infusion-associated AEs.

Symptomatic treatment (e.g., antipyretics, antihistamines, beta-agonists, oxygen, IV fluid) may be administered to subjects who experience immediate infusion-associated AEs. Following the appearance of either immediate or delayed infusion-associated events, subsequent dosing of study drug may be pre-treated with diphenhydramine (1 to 1.25 mg/kg IV; maximum of 50 mg), ranitidine (50 mg IV), famotidine (0.5 mg/kg IV), dexamethasone (0.4 mg/kg IV; maximum of 20 mg), and/or acetaminophen (500 mg).

#### **9.4.9.1 Restricted Therapy and Medications**

Subjects with a previous orbital irradiation or surgery for TED or who have a planned orbital irradiation or surgery for TED over the course of this study are not eligible for study enrollment. In addition, oral corticosteroids, selenium, biotin, immunosuppressive agents, investigational agents, and illicit drug/alcohol use are restricted as shown in [Table 9.1](#).

**Table 9.1      Restricted Medications and Therapies**

Medication/Therapy	Restricted Dose or Time Period
Orbital irradiation for TED	Any history or planned procedure during entire study duration through Week 48 of Follow-Up Period.
Eye surgery for TED	Any history or planned procedure during entire study duration through Week 48 of Follow-Up Period.
Steroids for treatment of TED	Steroids (IV or oral) for treatment of TED and steroid eye drops are not allowed between Week 24 of the HZNP-TEP-301 protocol and Baseline/Day 1 of the HZNP-TEP-302 protocol through the end of study visit.
Steroids for conditions other than TED	Systemic steroid use (IV or oral) for conditions other than TED is not allowed during the study however topical steroids for dermatological conditions, inhaled steroids, and IV dexamethasone for infusion-associated AEs are allowed.
Non-steroid eye drops	Vasoconstrictor eye drops are not allowed during the study. Other non-steroid drops such as saline or methylcellulose are allowed but should not be used on the day of a clinic visit.
Selenium or biotin for TED	Selenium or biotin for TED is not allowed during the study. A multivitamin (taken maximally once daily) containing selenium and/or biotin is allowed.
Rituximab (Rituxan® or MabThera®) or tocilizumab (Actemra® or Roactemra®)	Any previous use or anticipated use during the study.
Non-steroid immunosuppressive agent (other than rituximab or tocilizumab)	Use of a non-steroid immunosuppressive agent is not allowed during the study.
Investigational agent	60 days prior to study entry through study completion.
Illicit drug/alcohol use	History of abuse within the past 2 years or abuse during study.

Hearing loss and/or ototoxicity is not considered to be an adverse event causally associated with the use of teprotumumab. However, it may be reasonable to avoid ototoxic medications such as systemic administration of aminoglycoside and platinum-based chemotherapy during the study.

The following medications may cause muscle spasm/cramps and should be avoided during the study: donepezil, neostigmine, and vincristine.

All concomitant treatment (for TED and other conditions) in the Treatment Period and the Follow-Up Period must be documented in the eCRF.

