#### 7.1.3.4.4 Pharmacodynamic Markers

#### 7.1.3.4.5 Safety

##### 7.1.3.4.5.1 River Vision TED01RV Study

Treatment-emergent AEs (TEAEs) in TED01RV that were reported for at least 5% of the subjects in the teprotumumab group and had a greater frequency than that in the placebo group are shown in [Table 7.2](#). The majority of AEs were mild, required no treatment, and resolved while subjects remained on drug. Hyperglycemia, which was monitored by assessing blood glucose and HbA1c, was the only AE clearly identified as related to study drug.

**Table 7.2 Summary of TEAEs Reported in at Least 5% of Subjects in Teprotumumab Treatment Group and % is Greater Than Placebo**

TEAEs	Placebo N=44 n (%)	Teprotumumab N=43 n (%)	Summary Details for TEAEs in Teprotumumab Group
Any TEAE	32 (72.7)	32 (74.4)	
Nausea	4 (9.1)	8 (18.6)	Generally mild and reported after first/second infusions
Muscle spasms	2 (4.5)	8 (18.6)	Intermittent, 2/8 cases experienced for >1 week and treated with muscle relaxants
Diarrhea	2 (4.5)	6 (14.0)	Treatment required in 2/6 cases, 1 designated an SAE (see below)
Hyperglycemia	2 (4.5)	5 (11.6)	Mechanism-based AE
Alopecia	2 (4.5)	3 (7.0)	All mild and no treatment required
Dry skin	0	3 (7.0)	All mild, one case used topical dry skin cream
Dysgeusia	0	3 (7.0)	For 2/3 cases a transient “metallic” taste on Days 1-2
Headache	2 (4.5)	3 (7.0)	Generally mild, one subject took paracetamol
Paresthesia	0	3 (7.0)	“Tingling” reported in nose, feet or chest; variable onset and in 2/3 cases occurred on 1 day
Hearing impaired	0	3 (7.0)	Disparate symptoms, onset and duration (i.e., one unilateral with onset 16 weeks after end of therapy, one mild bilateral that resolved, one intermittent in a subject with positive history of tinnitus)
Weight loss	0	3 (7.0)	Variable timing; decreases range from 5-9 lb.

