#### **9.5.4.1.1.5 Adverse Events of Special Interest**

Based on previous clinical experience in TED, the following AESIs are identified for this study (See [Section 7.1.3.4.5.5](#) for further information):

- Infusion reactions (e.g., nausea, vomiting, facial flushing, warmth, dyspnea, dizziness, hypertension, hypotension, pruritus)
- Hyperglycemia
- Muscle spasms
- Diarrhea

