### 9.5.4.1.4 Relationship to Study Drug

The relationship of the study drug to each AE will be determined by the Investigator and the Sponsor based on the following definitions:

- No reasonable causal relationship (probably not related): There is no plausible temporal relationship or there is another explanation that unequivocally provides a more plausible explanation for the event.
- Yes, reasonable causal relationship (possibly related): There is evidence in favor of a causal relationship (i.e., there is a plausible time course) and at least one of the following criteria apply:
  - There is a reasonable pharmacological relationship (or known class effect)
  - There is no other more plausible explanation
  - There is a positive de-challenge (without active treatment of the event)
  - There is a positive re-challenge
  - There is a distinguishable dose effect

Within the reporting requirement under 21 CFR 312.32(c)(1)(i), the FDA provides the following examples of types of evidence that would suggest a causal relationship between the drug and the AE.

- A single occurrence of an event that is uncommon and known to be strongly associated with drug exposure (e.g., angioedema, hepatic injury, Stevens-Johnson Syndrome).

- One or more occurrences of an event that is not commonly associated with drug exposure, but is otherwise uncommon in the population exposed to the drug (e.g., tendon rupture).
- An aggregate analysis of specific events observed in a clinical trial (such as known consequences of the underlying disease or condition under investigation or other events that commonly occur in the study population independent of drug therapy) that indicates those events occur more frequently in the drug treatment group than in a concurrent or historical control group.

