10.3. ADVERSE EVENTS

All adverse events will be coded using MedDRA version 20.1. The TEAE reporting period begins with administration of the first dose of study medication on HZNP-TEP-302 Day 1 and continues until 3 weeks (21 days) after the last dose of study drug. The Follow-Up AE reporting period begins 3 weeks (21 days) after the last dose of study drug through completion of the Follow-Up Period (Week 48 or PW).

Missing data conventions for AEs are described in Section 6.3.4.

An overall summary of TEAEs will be provided by treatment received in HZNP-TEP-301 and overall, including the number and percentage of subjects with each AE type as well as the number of events for each of the following:

- TEAEs

- Serious TEAEs
- Related TEAEs
- Related serious TEAEs
- TEAEs with an intensity of severe or higher
- TEAEs leading to interruption of study drug administration
- TEAEs leading to permanent withdrawal of study drug
- Related TEAEs leading to permanent withdrawal of study drug
- TEAEs leading to study discontinuation
- Related TEAEs leading to study discontinuation
- TEAEs leading to death

Additional TEAE summaries will be provided by treatment received in HZNP-TEP-301 and overall, including the number and percentage of subjects experiencing TEAEs for the following:

- TEAEs overall and by SOC and PT, including the following subgroup analyses:
 - Age (<65 years, ≥65 years)
 - Gender (male, female)
 - Race (white, black or African American, Asian, other)
 - Ethnicity (Hispanic or Latino, not Hispanic or Latino)
- Related TEAEs overall and by SOC and PT
- TEAEs by maximum intensity, overall and by SOC and PT
- Serious TEAEs, overall and by SOC and PT
- Related TEAEs by intensity, overall and by SOC and PT
- TEAEs leading to permanent withdrawal of study drug, overall and by SOC and PT

- TEAEs of special interest including potential infusion-related reaction, anaphylactic reaction, hearing loss, hyperglycemia, muscle spasm, and diarrhea (see Section 10.3.1), by SOC, PT and overall
- TEAEs of special interest with missing AE start times including potential infusion-related reaction of any type, infusion-related reaction excluding those of an anaphylactic nature, and anaphylactic reactions (see Section 10.3.1), by SOC, PT and overall

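### Protocol 9.4.9.1 tells sites that hearing loss is not considered causally associated with teprotumumab; the controlled data shown in the protocol cannot settle that, and the statement may pre-judge relatedness calls.

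*Protocol*

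**What the plan says.** The sentence at issue stands below Table 9.1, in Protocol Section 9.4.9.1: "Hearing loss and/or ototoxicity is not considered to be an adverse event causally associated with the use of teprotumumab". The next sentence adds a precaution: "However, it may be reasonable to avoid ototoxic medications such as systemic administration of aminoglycoside and platinum-based chemotherapy during the study".

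Protocol Table 7.2 (Section 7.1.3.4.5.1) reports hearing impairment in 3 teprotumumab subjects and no placebo subject in the earlier placebo-controlled TED study, TED01RV. It describes the three as "one unilateral with onset 16 weeks after end of therapy, one mild bilateral that resolved, one intermittent in a subject with positive history of tinnitus". The text introducing the table singles out hyperglycemia as the only event clearly identified as drug-related.

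Protocol Section 9.5.4.1.4 sets the rule for causality: "The relationship of the study drug to each AE will be determined by the Investigator and the Sponsor based on the following definitions". The criteria include time course, alternative explanations, de-challenge and re-challenge. Nothing there exempts hearing events.

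The two documents differ on events of special interest. Protocol 9.5.4.1.1.5 begins "Based on previous clinical experience in TED, the following AESIs are identified for this study" and names infusion reactions, hyperglycemia, muscle spasms and diarrhea; Section 7.1.3.4.5.5 gives the same four. SAP 10.3 plans to summarize "TEAEs of special interest including potential infusion-related reaction, anaphylactic reaction, hearing loss, hyperglycemia, muscle spasm, and diarrhea". SAP Section 12 does not record the addition of hearing loss.

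**The concern.** An investigator who has read that hearing loss is not considered drug-related has been given an answer before applying the 9.5.4.1.4 criteria to a particular patient. There is no concurrent control here. Subjects who had teprotumumab in the lead-in study may receive a second course, up to 8 + 8 = 16 infusions in all. A between-arm comparison therefore cannot compensate for under-attribution at the site.

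The items that depend on the relatedness call are:

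- **Tables.** The related, related-serious, related-withdrawal and related-discontinuation TEAE summaries (SAP 10.3).
- **Follow-up.** Drug-related events still ongoing at study termination (Protocol 9.5.4.1.6).
- **Severe-event provisions.** The dosing and discontinuation provisions in 9.3.3 and 9.4.6.3.2 that are worded for drug-related severe events.
- **Late SAEs.** SAEs seen after study completion, which the investigator reports when he or she believes the drug possibly caused them (9.5.4.1.2).

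**Working it through.** **Inputs (Protocol Table 7.2).** Hearing impaired: teprotumumab 3 of 43, placebo 0 of 44.

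**The table's figure.** 3/43 = 6.98%, which rounds to the printed 7.0%. 0/44 = 0%.

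**Fisher exact test.** With 3 events among 87 subjects, the probability that all fall on teprotumumab is (43 × 42 × 41)/(87 × 86 × 85) = 74,046/635,970 = 0.116. The opposite extreme, all on placebo, is (44 × 43 × 42)/635,970 = 0.125. That is more probable than the observed table, so it is not added. Two-sided p = 0.116. Barnard's exact test gives 0.086.

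**Intervals.** Clopper-Pearson 95%: 1.5% to 19.1% for 3/43, and 0 to 1 - 0.025^(1/44) = 8.0% for 0/44. For the difference (Newcombe), the Wilson limits are 2.4% to 18.6% and 0 to 8.0%:

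- lower: 7.0 - √[(7.0 - 2.4)² + 8.0²] = -2.3 points (unrounded inputs)
- upper: 7.0 + (18.6 - 7.0) = 18.6 points

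The data are compatible with no effect and with an excess of more than 18 points.

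**Sensitivity to the late case.** One case began 16 weeks after therapy. Without it the count is 2 vs 0, and p = (43 × 42)/(87 × 86) = 1,806/7,482 = 0.24. The protocol does not say how TED01RV defined a treatment-emergent event. Under this study's window of 21 days after the last dose, that case would not count as treatment-emergent. Counted from a Week 21 last infusion, such an event would fall at Week 21 + 16 = Week 37. That is inside the Follow-Up Period for lead-in non-responders. It is after the last clinic visit (Week 24) for relapse subjects, whose later contacts ask about TED treatment.

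**What depends on relatedness.**

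| Depends on it | Does not |
|---|---|
| Related-TEAE summaries (SAP 10.3) | All-TEAE, serious-TEAE and withdrawal summaries (SAP 10.3) |
| Follow-up of ongoing drug-related events (9.5.4.1.6) | Hearing-loss AESI table, built from MedDRA terms (SAP 10.3.1) |
| Drug-related severe-event provisions (9.3.3, 9.4.6.3.2) | SAE reporting and follow-up, consent to 30 days after discharge (9.5.4.1.5) |
| SAEs after study completion (9.5.4.1.2) | Follow-up of subjects who discontinue for an AE (9.3.3) |

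**The case against.** The strongest reply is that the sentence agrees with the protocol's own reading of TED01RV. The cases differ in laterality, timing and history, and only hyperglycemia was called clearly related. Table 7.2 lists only events reported in at least 5% of the teprotumumab group and more often than on placebo, so every row is an imbalance by construction. Dry skin, dysgeusia, paresthesia and weight loss show the same 3 vs 0. This stands: a reader might infer that the sentence contradicts the table, and it does not. An event not clearly identified as related is still not an event shown to be unrelated.

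The wording reports what is considered to be so, and its basis may lie outside Table 7.2. The oncology program treated over 700 subjects, its safety data are summarized in the Investigator's Brochure, and parts of 7.1.3.4.5 are redacted. This also stands. The conclusion can only be that the controlled data shown do not support the sentence, not that nothing does.

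The sentence introduces a concomitant-medication precaution and is not part of the causality instructions. The Sponsor also judges relatedness, and SAP 6.3.4 counts a missing relationship as related. These points limit the concern. The Sponsor's assessment is only partial protection, since the statement is in the Sponsor's own protocol.

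A reader might also take the SAP's listing of hearing loss as an event of special interest as evidence against the sentence. That status calls for closer summary and does not imply causation. The protocol says SAP analyses supersede its own, so the difference between the lists is a matter of alignment.

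**Conclusion.** The point holds in a limited form. A site-facing statement of no causal association is stronger than 3/43 vs 0/44 can support, and it may lead to under-attribution of hearing events. The affected outputs and provisions are those that depend on relatedness. For follow-up, that leaves mainly events that are neither serious nor the reason for discontinuation.

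Three stronger readings are not supported. The documents do not show that teprotumumab causes hearing loss. They do not show that relatedness calls were biased; they show only a route by which they could be. Nor would hearing events vanish from the safety report, because the term-based hearing-loss table and the all-event summaries capture recorded events whatever the causality call.

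The conclusion assumes that investigators read the statement as guidance on causality. It also assumes that no evidence in the Investigator's Brochure or the redacted text settles the question. Neither can be checked from the documents.

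**What to change.** Remove the causal statement from Protocol 9.4.9.1, or reword it to say that an association has not been established. Direct sites to judge each hearing event on its own facts under 9.5.4.1.4. If the sponsor holds evidence that justifies the present wording, the section should cite it. The precaution about ototoxic drugs is a clinical matter and is outside this point.

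As housekeeping, reconcile the AESI lists in Protocol 7.1.3.4.5.5 and 9.5.4.1.1.5 with SAP 10.3.1, and note the addition in SAP Section 12. This would not justify a change on its own.

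The cost is one sentence and a communication to sites, with no new procedure, sample or analysis. Related-event counts may become slightly less favourable. SAP 2.2 describes the integrated safety summary and its 120-day update as already done, so some relatedness calls predate any change. They stay as they are unless hearing events are re-reviewed.
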